3- Female patients must always be informed about the teratogenic risk [5] and required to use two forms of contraception, starting one month before therapy and continuing for one-month post therapy[6]. Patients should be educated about appropriate forms of birth control since some types are unacceptable, such as the female condom and progesterone-only birth control pills (primary forms of birth control: tubal sterilization, vasectomy, intrauterine device, and combination hormonal therapy. Secondary structures of contraception: condoms, diaphragms, cervical caps, and vaginal sponges containing spermicide).

*they have to make monthly pregnancy test while taking isotretinoin.

To reduce fetal exposure to isotretinoin, Clinical pharmacists should encourage the use of iPLEDGE, a risk management program to regulate the use of isotretinoin, Available at <https://www.ipledgeprogram.com/iPledgeUI/home.u>, and its goal to ensure that women using isotretinoin do not become pregnant and women who are pregnant do not use isotretinoin.

4- Do not breastfeed while taking isotretinoin and for one month after stopping it. Isotretinoin may pass through the milk and harm the baby[7].

5- There are important warnings must be mentioned:

- vitamins :(do not take vitamin A),
- antibiotics: (Do not take tetracyclines, may increase the pressure in the brain with isotretinoin),
- lenses: (may make irritation), so avoid using it as much as possible
- blood donation: (It is not possible to donate blood for at least one-month post therapy for fear of giving your blood to a pregnant woman, causing congenital diseases in the fetus.),
- waxing and laser hair removal: may cause pigmentation and skin irritation, so it should be avoided during treatment and 6 months after stopping the drug(preferred).
- Cosmetics: (Do not use cosmetic procedures to smooth your skin; it may increase your chance of scarring or inflammation of the skin from these procedures).
<https://www.medicines.org.uk/emc/product/3870/pil> (isotretinoin leaflet).

6- Isotretinoin may cause depression, psychosis, and violent behavior; particular care needs to be taken in a patient with a history of depression, and all patients should be monitored for signs of depression and referred for appropriate treatment if necessary. A further psychiatric or psychological evaluation may be necessary. (leaflet)

7- Take it with food or after food, and it prefers to take with fatty meals, store at room temperature. (leaflet)

8- Isotretinoin may cause pain in the muscles or joints, especially for adolescents who undergo vigorous exercise. Painkillers can be taken in this case, such as non-steroidal analgesics or paracetamol. (leaflet)

9- Do not use two doses at one time if you missed the dose (isotretinoin leaflet).

10 - Do not share isotretinoin with other people. It can cause congenital disabilities and other serious health problems. (leaflet)

11- Inform the doctor or pharmacist of any medicine that you will take during treatment with isotretinoin, because drug interactions may occur. (Leaflet)

Appendix 3

A. Baseline questionnaire

General information			
Age:			
Marital status:	Gender:		
 Single  Married	 female  Male		
Educational level:			
 Basic  Secondary  High school  Diploma  Bachelor  Master  PHD			
Residential area:			
 Irbid  Amman  Al Zarqa  Al Mafraq  Al Balqaa  Al Karak  others, Mention			
Profession:			Weight (Kg) Hight (cm)
 Medical Profession  Non-medical profession  Student  Doesn't work			
Monthly income:	 less than 500 JD  500-1000  above 1000		
Do you have health insurance?	 yes		 No
Current dose of isotretinoin medication:			
 Number of capsules:  number of times:  strength:			
Period since the initiation of isotretinoin medication:			
 Newly diagnosed  1 month  2 months  3 months  4 months, others			

Please answer the following questions about your current of isotretinoin:

1. Do you have chronic diseases?

- Pressure
- Diabetes
- Thyroid gland

Other.....

2. Have you been asked for the following laboratory tests?

Pregnancy test: - yes - no -not applicable

Liver function test: - yes -no

Lipid profile test: - yes -no

3. Did you make liver function test and lipid profile test before starting treatment?

Yes

No

4. Have you ever used isotretinoin without prescription even for one time?

Yes

No

5. Is it your first visit to a dermatologist to acne?

Yes

No

6. Did anyone explain to you about the medicine?

Yes

No

- Please specify who explained to you about the medicine?

Doctor

Pharmaceutical

The doctor and the pharmacist.

Otherwise.

7. How much does acne affect your daily, psychological and social life?

Very big impact.

Big impact

Medium

Weak

There's no effect.

8. What do you think your acne is?

Mild < 30 black and white pills

Moderate ~ 100 black and white pills

- Severe nodules, big, painful red pills.
- Very severe (there are scar scars, pigments and old raisins)

Please answer the following knowledge questions:

9. Which of the following is isotretinoin side effect?

- Dryness Teratogenicity Abnormal lipid profile
- Constipation difficulty in breathing back pain Others

10. (In case of using isotretinoin based on medical prescription), the physician had explained for me isotretinoin side effects and how to manage them:

- Yes
- No

11. Isotretinoin can be used without prescription:

- Yes
- No
- I do not know

12. Isotretinoin can be used during some periods of pregnancy:

- Yes
- No
- I do not know

13. There is no need to have laboratory tests during isotretinoin therapy:

- Yes
- No
- I do not know

14. It is recommended to drink plenty of water during isotretinoin therapy to avoid dryness:

- Yes
- No
- I do not know

15. It is recommended to use sun block during isotretinoin therapy:

- Yes

- No
- I do not know

16. It is recommended to take isotretinoin after fatty meals:

- Yes
- No
- I do not know

17. Blood donation is allowed during isotretinoin therapy:

- Yes
- No
- I do not know

18. Breast feeding is allowed during isotretinoin therapy:

- Yes
- No
- I do not know

19. wax and laser for hair removal is allowed during isotretinoin therapy:

- Yes
- No
- I do not know

For married female. kindly answer the following questions

20. Do you use contraception method during your isotretinoin therapy?

- Yes
- No

21. Did you have pregnancy test before starting isotretinoin therapy?

- Yes
- No

22. Did your doctor explain for you the teratogenicity of isotretinoin?

- Yes
- No

23. Did the pharmacist explain for you the teratogenicity of the drug?

- Yes
- No

24. Did your doctor request you to sign up consent form which explain to you the isotretinoin side effects?

- Yes

No

25. (In case of using isotretinoin based on medical prescription), the doctor has explained to me the importance of using two contraceptive methods during isotretinoin therapy:

Yes

No

26. Do you think you needed to explain more about the drug in general?

Yes

No

27. Do you think you needed to explain more about the drug in terms of the method of use?

Yes

No

28. Do you think you need edited more explanations about the side effects of the drug and how to avoid it?

Yes

No

29. Do you have any feedback regarding this questionnaire?

Yes

No

Measure of the HADS score:

I'm frustrated.	D	I feel confused.	A
Always	3	Always	3
Often	2	Often	2
Sometimes	1	Sometimes	1
At all	0	At all	0
I'm scared.	A	I still enjoy the things I used to enjoy.	D
Always	3	Always	0
Often	2	Often	1
Sometimes	1	Sometimes	2
At all	0	At all	3
I lost interest in my appearance.	D	I feel kind of afraid something bad is going to happen.	A
Always	3	Always	3
Often	2	Often	2
Sometimes	1	Sometimes	1
At all	0	At all	0
I'd like to have fun and look forward to enjoying things.	D	I can laugh and see the funny side of things.	D
Always	0	Always	0

Often	1	Often	1
Sometimes	2	Sometimes	2
At all	3	At all	3
I suddenly feel shaking.	A	Disturbing thoughts are in my mind.	A
Always	3	Always	3
Often	2	Often	2
Sometimes	1	Sometimes	1
At all	0	At all	0
I can enjoy a book or tv show.	D	I feel happy.	D
Always	0	Always	0
Often	1	Often	1
Sometimes	2	Sometimes	2
At all	3	At all	3
I can sit down easily and feel comfortable.	A	I feel unstable.	A
Always	0	Always	3
Often	1	Often	2
Sometimes	2	Sometimes	1
At all	3	At all	0

B. Follow-up questionnaire

1. Have there been any changes in the dose? (Number of tablets / concentrate)

- Yes
- No

2. What are the results of previous tests?

- LFT: - Normal - high - low
- lipid profile: - normal -high -low

3. Have you been asked to do new tests for this month (after three months of treatment):

- Pregnancy test: - yes - no -not applicable
- Liver function test: - yes -no
- Lipid profile test: - yes -no

4. Do you consult your doctor or pharmacist before using any other medications or dietary supplement during isotretinoin therapy?

- Always 100%
- often 70%

- Sometimes 50%
- Rarely 20%
- Never 0%

5. During your treatment period, did you seek help from outside sources for obtaining information about the medication?

- Yes
- No

- What are the sources?

- Internet
- Social networking sites
- Leaflet
- Relatives or friends
- Other.....

6. Do you have follow-up visits at regular basis with your physician?

- Yes
- No

- If the answer is “Yes” for the previous question. kindly specify follow-up period:

- every month
- every two months
- every three months
- More than three months

7. In your opinion, how much is the improvement of your disease (acne)?

- Excellent
- Very good.
- It's good.
- Acceptable
- Weak

Please answer the following knowledge questions:

8. Which of the following is isotretinoin side effect?

Dryness Teratogenicity Abnormal lipid profile
 Constipation difficulty in breathing back pain Others

9. (In case of using isotretinoin based on medical prescription), the physician had explained for me isotretinoin side effects and how to manage them:

Yes
 No

10. Isotretinoin can be used without prescription:

Yes
 No
 I do not know

11. Isotretinoin can be used during some periods of pregnancy:

Yes
 No
 I do not know

12. There is no need to have laboratory tests during isotretinoin therapy:

Yes
 No
 I do not know

13. It is recommended to drink plenty of water during isotretinoin therapy to avoid dryness:

Yes
 No
 I do not know

14. It is recommended to use sun block during isotretinoin therapy:

Yes
 No
 I do not know

15. It is recommended to take isotretinoin after fatty meals:

Yes
 No
 I do not know

16. Blood donation is allowed during isotretinoin therapy:

Yes
 No
 I do not know

17. Breast feeding is allowed during isotretinoin therapy:

- Yes
- No
- I do not know

18. wax and laser for hair removal is allowed during isotretinoin therapy:

- Yes
- No
- I do not know

For married female, kindly answer the following questions

19. Do you use contraception method during your isotretinoin therapy?

- Yes
- No

20. Did you have pregnancy test before starting isotretinoin therapy?

- Yes
- No

21. Did your doctor explain for you the teratogenicity of isotretinoin?

- Yes
- No

22. Did the pharmacist explain for you the teratogenicity of the drug?

- Yes
- No

23. Did your doctor request you to sign up consent form which explain to you the isotretinoin side effects?

- Yes
- No

24. (In case of using isotretinoin based on medical prescription), the doctor has explained to me the importance of using two contraceptive methods during isotretinoin therapy:

- Yes
- No

25. How well do you stick to the instructions to avoid medication-related side effects?

- Excellent
- Very good.
- It's good.
- Acceptable
- Weak

26. What is the impact of the side effects on your daily life and your usual activities?

- Big effect
- moderate effect

- Weak effect
- There's no effect.

27. Was the menstrual cycle affected during treatment?

- Yes
- No

- If yes, what is the impact?

- getting late
- getting early
- became heavy
- became light
- its duration became longer
- its duration became shorter

28. Was your treatment affected during the Corona period?

- Big effect
- moderate effect
- Weak effect
- There's no effect.

- If yes, what is the impact?

- Getting the medication
- adherence to medication
- Going for monthly doctor reviews
- adherence to periodic tests

29. Do you think you needed to explain more about the drug in general?

- Yes
- No

30. Do you think you needed to explain more about the drug in terms of the method of use?

- Yes
- No

31. Do you think you need edited more explanations about the side effects of the drug and how to avoid it?

- Yes
- No

32. Do you have any feedback regarding this questionnaire?

- Yes

No

Please answer the following questions regarding adherence to recommendations provided by clinical pharmacist.

	yes	no	I do not know	Not applicable
I adhere to drink plenty of water during isotretinoin use				
I adhere to use eye drop during isotretinoin use				
I adhere to use lip balm during isotretinoin use				
I adhere to use body lotion during isotretinoin use				
I adhere to make laboratory monitoring (AST & ALT) during isotretinoin				
I adhere to make lipid profile test during isotretinoin use				
I adhere to use sunblock when going out during isotretinoin use				
I adhere to take isotretinoin with fatty foods				
I adhere not to donate blood during isotretinoin use				
I adhere not to make laser or wax during isotretinoin use				
I adhere not to breastfeed my child during treatment:				
I adhere to do a monthly pregnancy test				

Please answer the following questions regarding adherence to the medication?

	At all	Rarely	Sometimes	Usually,	Always
Do you forget to take your meds?					
Do you skip medication when you feel better?					
Do you skip taking medications when they're worse after taking medications?					
Have you run out of your medications?					
In general, do you adhere to what your doctor or pharmacist tells you about your lifestyle (food, exercise, smoking...) I don't think					
Can you please tell us what are the most common reasons for not taking your medications?					

Measure of the HADS score:

I'm frustrated.	D	I feel confused.	A
Always	3	Always	3
Often	2	Often	2
Sometimes	1	Sometimes	1
At all	0	At all	0
I'm scared.	A	I still enjoy the things I used to enjoy.	D
Always	3	Always	0
Often	2	Often	1
Sometimes	1	Sometimes	2
At all	0	At all	3
I lost interest in my appearance.	D	I feel kind of afraid something bad is going to happen.	A
Always	3	Always	3
Often	2	Often	2
Sometimes	1	Sometimes	1
At all	0	At all	0
I'd like to have fun and look forward to enjoying things.	D	I can laugh and see the funny side of things.	D
Always	0	Always	0
Often	1	Often	1
Sometimes	2	Sometimes	2
At all	3	At all	3

I suddenly feel shaking.	A	Disturbing thoughts are in my mind.	A
Always	3	Always	3
Often	2	Often	2
Sometimes	1	Sometimes	1
At all	0	At all	0
I can enjoy a book or tv show.	D	I feel happy.	D
Always	0	Always	0
Often	1	Often	1
Sometimes	2	Sometimes	2
At all	3	At all	3
I can sit down easily and feel comfortable.	A	I feel unstable.	A
Always	0	Always	3
Often	1	Often	2
Sometimes	2	Sometimes	1
At all	3	At all	0

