After the informed consent (see appendix 1) is taken from each patient who agreed to participate in the study, the participants will be randomly assigned to either an intervention group or a control group. Intervention group will consist of the patients who will receive the educational process (recommendations) about isotretinoin by clinical pharmacists additionally to the usual routine care (education about isotretinoin provided by the physician). Control group will consist of the patients who will receive the usual routine care. Both patients and physicians are unaware of patients' assignment in both groups.

The main task of the clinical pharmacist is to educate patients in intervention group by providing them all information about isotretinoin that can serve the patient during the treatment period, which includes: the degree of the importance of adherence to the drug and the recommendations, the correct method of taking it, the importance, and when, of doing periodic laboratory tests (lipid profile, liver enzyme test, and pregnancy test), and explanation of common side effects, how to avoid and deal with them, and what are the cases in which the drug should be stopped. The detailed information on the recommendation for managing side effects that will be used to educate the patients are provided in Appendix 2.

Patient's adherence to the recommendations, awareness and side effects managements for both groups will be measured through a set of questions adapted from a validated questionnaire after one month and three months of isotretinoin initiation (Appendix 3). The validated questionnaire was adopted from a previous study on patients' knowledge about isotretinoin therapy use in Jordan. The permission to use the questionnaire was obtained from the researcher.

The questionnaire is composed of 41 questions related to: demographics, side effects, physician and clinical pharmacist practice, recommendations and contraindications according to current guidelines, and patients' commitment. In addition, the Hospital Anxiety and Depression Scale (HADS) [22], will be used to evaluate depressive and anxiety symptoms at baseline and during the follow up period in each group. Finally, clinical improvement in acne will be evaluated three months after initiating the treatment from the view of physicians as well as the patients themselves.

Location and safety considerations

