The dermatology clinics located in: King Abdullah University Hospital (KAUH), in Princess Basma Hospital, (PBH), King Talal Hospital (KTH), Princess Haya Hospital (PHH) and Prince Rashid Hospital (PRH) and King Hussein Medical Center will be visited for patients interview and data collection. The participants' privacy will be preserved throughout the study and the participants' answers will be kept strictly confidential and never associated with any personal details. This study does not involve any human biological sample. No potential risks will be associated with the participation in the current study. No special safety consideration for isotretinoin drug Except those mentioned above since it approved from 1982. Consent will be obtained from IRB.

Data analysis

After data was collected, the data was entered into Excel worksheets. The responses were coded and entered into SPSS (version 23). Descriptive statistics of categorical and continuous variables were

calculated. For the categorical variables, the frequency and percentage were calculated, while the arithmetic mean and standard deviation were calculated for continuous variables.

The differences in participants' responses were examined using the Chi-square test (between intervention and control groups) and McNamara's test (between baseline and follow up encounters) for categorical dependent variables as appropriate. For continuous dependent variables, One Way Analysis of Variance (ANOVA) test, independent samples t-test, and Wilcoxon test were performed when applicable. Both Kolmogorov-Smirnov Z and Shapiro-Wilk tests were used to test for normality of continuous variables. The statistical significance level was considered at a p-value ≤ 0.05 .

Patients Knowledge and Awareness of Isotretinoin:

The degree of knowledge and awareness of correct practice was calculated as a total score. The patient knowledge section consisted of ten different questions/items, and each item had two answers (yes/no). Items were coded according to the answer; the correct (adequate) answer was coded as one (1), while the wrong (not adequate) answer was coded as zero (0). So, the knowledge score could take the values of 0 (no knowledge) to 10 (perfect knowledge).

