HADS scores were categorized into three categories based on the abnormality classification; normal (less than eight), borderline abnormal (between eight and eleven) and abnormal (above eleven). Chi square test was used to evaluate the association between HADS score categories and intervention control status at baseline and at follow up.

Patients Adherence to Medication

The percentages (%) of patients' adherence to medication and non-pharmacological adherence were calculated by dividing the number of adherent patients by the total number of patients in both groups. According to the final question, the reasons behind the patient's non-adherence were themed into three distinct groups (forgetfulness, run out, and unavailability of isotretinoin). The frequency (%) of each group was calculated by dividing the number of times each category has occurred over the total number of patients and multiplying by 100. Chi-square test was conducted to evaluate the association between adherence status and patient intervention control status.

Results

1. Baseline Questionnaire Results

A total of 207 patients using isotretinoin in Jordan were randomly recruited to participate in the study. About four patients missed answering the phone in the follow-up phase, so they were excluded from the study. The response rate was 96.7% and 203 patients completed the study as shown in **Figure 1**.

[figure not shown]

Figure 1: Patient recruitment flowchart

1. Demographics of Respondents

The demographics of the participants are summarized in **Table 1**. All baseline demographic and clinical characteristics of the study participants were not statistically different between intervention and control group except for monthly income with P -value=0.032. Most respondents were female ($n=179$, 88.2%) compared to male ($n=24$, 11.8%) in both groups. Most of the patients were in the age group of 18-25 years, and the $mean \pm SD$ of age for the intervention group was 21.68 ± 3.21 and 21.36 ± 2.6 for the control group. Regarding marital status, 96.9% of the participants were single

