	99 (96.1)	103 (100)	0.045	99 (99)	99 (99)	0.317
It is preferred to take isotretinoin with fatty foods						
	70 (68)	103 (100)	< 0.001	74 (74)	81 (81)	0.0196
We can donate blood during isotretinoin*						
	36 (35)	103 (100)	< 0.001	30 (30)	43 (43)	0.0008
Woman can lactate while using isotretinoin*						
	31 (30.1)	94 (91.3)	< 0.001	28 (28)	40 (40)	0.0027
we can make laser or wax during isotretinoin*						
	37 (35.9)	98 (95.1)	<0.001	45 (45)	60 (60)	0.0011

Frequencies and percentages presented are for correct answers.

At follow-up, patients were asked if they searched for outside sources for information about the drug during their treatment. About 56% of the control group compared to 45% of the intervention group said yes with P-value=0.079.

4. Patient's Adherence to Recommendations About the Proper Use

The patient's adherence to recommendations for the proper use of isotretinoin and the adherence to

specific instructions on managing side effects provided by the physician or clinical pharmacist at follow-up was evaluated. The average recommendation score was 7.601 ± 1.358 for all patients, and it was significantly different between control and intervention group (the mean for intervention group= 8.534 ± 0.905 and control group= 6.64 ± 1.039) with P-value <0.001 . The percentage of participants who were adherent to all recommendations (10 out of 10) was 15.5% for the intervention group compared to 0% for the control group.

The frequency and number for patients who were adherent to the recommendations for the intervention group and control group are summarized in **Table 4.5**. Around 59% of the intervention group compared to 27% of the control group were adherent to drinking plenty of water (more than two liters per day) with P-value <0.001 .

Table 5: Patient's adherence to recommendations about the proper use at follow-up

	Intervention group n (%)	Control group n (%)	P value
I adhere to drink plenty of water during isotretinoin use			
yes	61 (59.2)	27 (27)	< 0.001
no	42 (40.8)	73 (73)	
I adhere to use eye drop during isotretinoin use			
yes	89 (86.4)	69 (69)	0.003
no	14 (13.6)	31 (31)	
I adhere to use lip balm during isotretinoin use			
yes	101 (98.1)	98 (98)	0.90
no	2 (1.9)	2 (2)	
I adhere to use body lotion during isotretinoin use			
yes	48 (46.6)	28 (28)	0.006
no	55 (53.4)	72 (72)	
I adhere to make laboratory monitoring (AST & ALT) during isotretinoin use			
yes	102 (99)	98 (98)	0.618
no	1 (1)	2 (2)	

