In the follow-up questionnaire, multiple additional questions were asked regarding patients' opinion about acne improvement, the impact of side effects on their daily activities, and their satisfaction with the provided drug information. There were statistically significant differences in all these three dimensions between the intervention and control groups.

About 47% of the patients who received the educational process from the clinical pharmacist in addition to the doctor reported that they had an excellent improvement in their acne conditions compared to 30% of the patients who received the educational process from the doctor only, P-value =0.048. Results are shown in **Table 10**.

Table 10: Patient's opinions about the improvement of the acne

	Intervention group n (%)	Control group n (%)	P value
In your opinion, how much is the improvement of your acne			
Excellent	48 (46.6)	30 (30)	0.048
very good	50 (48.5)	56 (56)	
good	5 (4.9)	5 (5)	

There was a significant difference between the intervention group and the control group with regards to the impact of side effects on daily life and normal activities of the patients, P-value<0.001. 76.6% of patients in the intervention group reported no effect or a weak effect on daily activity compared to 48% of the patients in the control group as indicated in **Table 11**.

Table 11: Patient's responses about side effect and their impact on daily activity

	Intervention group n (%)	Control group n (%)	P-value
How does the side effects affect your daily life and your normal activities			
Big impact	0 (0)	4 (4)	< 0.001
Moderate impact	24 (23.3)	48 (48)	
Weak impact	73 (70.9)	46 (46)	
There is no impact	6 (5.8)	2 (2)	

There are three questions about the patient's satisfaction with the provided drug information (either through the usual care provided by the doctor or the additional care provided by the clinical pharmacist in addition to the doctor). There were significant differences between the two groups with more satisfaction for the intervention group; 0% of the intervention group compared to 52% of the control group said they need more explanation about the drug with P-value<0.001. In addition, none of the intervention group compared to 71% of the control group said they need more

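### The protocol says patients are unaware of their assignment, but only one arm gets a pharmacist education session and no masking is described; correct the statement and label patient-answered outcomes as unblinded

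*Combined protocol and SAP*

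**What the plan says.** The Patients section of the combined protocol and SAP describes consent first ("After the informed consent (see appendix 1) is taken from each patient who agreed to participate in the study") and random assignment after it. The intervention group receives the "educational process (recommendations) about isotretinoin by clinical pharmacists additionally to the usual routine care"; the control group receives usual care alone. The paragraph ends by stating "Both patients and physicians are unaware of" assignment in either group.

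Adherence, awareness and side-effect management are measured by questionnaire, and mood by the HADS. Acne improvement was to be judged by physicians and by patients. Under Location and safety considerations, the clinics "will be visited for patients interview and data collection". Results 1 indicates telephone follow-up: "About four patients missed answering the phone in the follow-up phase". The text does not say whether interviewers knew the group.

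In Appendix 3 B, the follow-up form heads its adherence-to-recommendations items as concerning recommendations given by the clinical pharmacist. Results 4 reports of the resulting score that "it was significantly different between control and intervention group".

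**The concern.** The blinding statement and the description of the two arms do not fit together. A patient who has sat through a pharmacist's session knows it happened, and nothing comparable was arranged for the control arm. The follow-up form then reminds the respondent of the pharmacist just before asking about adherence.

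An open education trial is not at fault for being open. The harm lies in the claim. A reader who accepts it would set aside the possibility that people taught a list of recommendations report following that list more readily than people who were not. The claim would also carry into any risk-of-bias assessment of the trial.

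**Working it through.** **1. What the text supports, group by group**

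| Said to be unaware | What the documents describe | Reading |
|---|---|---|
| Intervention patients | Attend a pharmacist session; the form refers to the pharmacist's recommendations | Wrong as written |
| Control patients | Usual care only; no sham; no account of what they were told | Unsupported |
| Physicians | Pharmacists deliver the session, so masking is feasible; no procedure given | Unsupported |

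Interviewers and analysts are not mentioned.

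**2. Adherence-to-recommendations score (Results 4, Table 5)**

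Inputs: 8.534 (SD 0.905, n=103) and 6.64 (SD 1.039, n=100). The Table 5 yes-counts reproduce the means: 879/103 = 8.53 and 665/100 = 6.65.

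- Pooled SD = √[(102×0.905² + 99×1.039²)/201] = 0.973.
- SE = 0.973×√(1/103 + 1/100) = 0.1366.
- Difference = 8.534 − 6.64 = 1.894; t = 1.894/0.1366 = 13.9.
- 95% CI = 1.894 ± 1.972×0.1366 = 1.62 to 2.16.

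Net over-reporting of about 1.62 points in the intervention arm would be needed to remove significance (P=0.046 after subtracting 1.62, P=0.055 after 1.63). That is the lower confidence limit read another way, not an estimate of bias. Lip balm, AST/ALT, lipid test and sunblock are near ceiling and contribute only 0.00 + 0.01 + 0.01 + 0.04 = 0.06. The 1.62 would therefore have to come from the other six items, at 1.62/6 = 0.27, or 27 percentage points each on average.

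**3. Patient-rated acne improvement (Results 8, Table 10)**

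Printed counts for Excellent, Very good and Good are 48/50/5 (sum 103) and 30/56/5 (sum 91, with percentages on 100). Nine control answers are therefore not visible. The form also offers two lower grades. The printed rows alone give chi-square 3.77 on 2 df, P=0.15, which is not the reported value.

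Assume that control Very good is 65, with 56 a digit transposition. The control column then sums to 100. With expected count = row total × column total / 203, the intervention expectations are 39.58, 58.35 and 5.07, and the control expectations 38.42, 56.65 and 4.93. Chi-square = 1.793 + 1.195 + 0.001 + 1.847 + 1.231 + 0.001 = 6.07 on 2 df, P=0.048, as reported.

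The table shows how many intervention answers must move from Excellent to Very good before P exceeds 0.05:

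| Control answers assumed | P as answered | Answers needed |
|---|---|---|
| 30/65/5 (reproduces the reported P) | 0.048 | 1 (P=0.067) |
| Excellent v rest, 30/70 | 0.015 | 4 (P=0.060) |
| 30/56/14 (missing nine all Good) | 0.013 | 7 (P=0.0515) |
| 30/56/5/9 (missing nine in one lower grade) | 0.004 | more than 9 (P=0.017 after 9) |

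**4. HADS (Results 5)**

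The change scores do not differ (P=0.238 anxiety, P=0.323 depression). Two follow-up items do, with more intervention patients in the worse grades. Feeling tense a lot or most of the time: (4+20)/103 = 23.3% v (2+7)/100 = 9% (item P=0.006). Looking forward definitely less or hardly at all: (31+1)/103 = 31.1% v (16+1)/100 = 17% (item P=0.012). Differential reporting could enlarge or hide differences like these, so the caution cannot depend on which arm looks better.

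**The case against.** The best defence is that knowing one was taught by a pharmacist is not the same as knowing one's trial assignment. An intervention patient might take the session for ordinary clinic care, and a control patient might not know that another arm existed. What patients were told is in the consent form, which is not in the public file. This has force for control patients. For patients who attended the session, it could at most support a narrower claim, that the hypothesis or the other arm's care was concealed.

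Two pieces of apparent support are weak and are not relied on. The follow-up question "Did the pharmacist explain for you the teratogenicity of the drug" also appears on the baseline form, could refer to any pharmacist, and went only to married women, of whom there were seven. The description of the satisfaction items as covering information given "either through the usual care provided by the doctor or the additional care provided by the clinical pharmacist in addition to the doctor" is the results text's own gloss; the explanation items on the form name neither profession.

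It is also fair that the adherence difference is too large for its direction to be in much doubt, and that physicians may in fact have been masked.

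**Conclusion.** The patient-blinding statement is wrong as written for patients given the session, and unsupported for control patients and physicians. The patient-answered comparisons should be read as unblinded.

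The documents give no estimate of reporting bias. For adherence to recommendations, the size (1.89 points, 95% CI 1.62 to 2.16) is at risk more than the sign. The acne result is fragile on the reading that reproduces its P value, but that reading assumes a misprinted count. Across the readings tried, the answers needed run from one to more than nine.

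A reader might infer more than this, and the documents do not support it:
- *That over-reporting occurred, or explains the adherence result.* Nothing in the text shows either.
- *That physicians knew the assignment.* No procedure is given, but masking was feasible.
- *That the reported P=0.048 is an error.* It follows exactly under one plausible reading of Table 10.
- *That only favourable outcomes need the caution, or that the two HADS items show harm.* Bias can run either way. Those items are two of fourteen unadjusted follow-up comparisons, and the change scores do not differ.

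**What to change.** Replace the blinding sentence with: *Patients and clinical pharmacists were not blinded to the education received.* If the consent form concealed the hypothesis or the other arm's care, state that and no more. Claim masking of physicians, interviewers or analysts only where a procedure existed, and describe it; otherwise say there was none.

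Label adherence to recommendations, medication adherence, side-effect impact, satisfaction, patient-rated acne improvement and HADS as unblinded self-report. Label the knowledge score as an unblinded, patient-answered test, since its ten items are scored right or wrong. State that reporting may bias all these comparisons in either direction, whatever result was observed. Give the full distribution behind Table 10, so that the strength of the acne result can be judged.

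The cost is wording and one completed table. Sample size and analysis are unchanged. The conclusion has to be worded less strongly.
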